2.1 Intended Use

The FARAPULSE Pulsed Field Ablation System is indicated for the treatment of drug resistant, symptomatic persistent atrial fibrillation.

The FARAWAVE Catheter is indicated for the isolation of pulmonary veins and posterior wall in the ablation of drug resistant, symptomatic persistent atrial fibrillation.

2.2 Investigational Devices

2.2.1 FARAPULSE Pulsed Field Ablation System

The FARAPULSE Pulsed Field Ablation (PFA) System is comprised of the following. The full list of components is provided in **Table 2.2-1**.

- FARAWAVE Pulsed Field Ablation Catheter (FARAWAVE PFA Catheter)
- FARASTAR Catheter Connection Cable
- FARASTAR Pulsed Field Ablation Generator and associated cables
- Recording System Module and associated cables
- FARADRIVE Steerable Sheath

The FARAPULSE Pulsed Field Ablation System is currently commercialized in Europe and indicated for the treatment of Paroxysmal Atrial Fibrillation. The commercial system will be used for the study outside of its CE Mark scope. The investigational systems used in North America and in Europe are functionally equivalent.

[figure not shown]
A copy of the device labeling and DFU/IFU will be provided in local language(s) as required per national regulations, as well as the Investigator Brochure.

Table 2.2-1: Components of the FARAPULSE Pulsed Field Ablation System

Component	Subcomponents
FARAWAVE PFA Catheter	1. FARAWAVE Pulsed Field Ablation Catheters (31mm and 35mm) 2. FARASTAR Catheter Connection Cable
FARASTAR PFA Generator and Related Equipment	1. FARASTAR Pulsed Field Ablation Generator 2. FARASTAR Recording System Module Sub-components of the FARASTAR Generator and RSM:* 3. FARASTAR Stimulation Module Cable 4. FARASTAR Recording System Module Catheter Pin Cable 5. FARASTAR EGM Cable for FARAWAVE 6. FARASTAR Recording System Module ECG Trunk Cable 7. FARASTAR Recording System Module ECG Output Module 8. FARASTAR Recording System Module EGM Input Module 9. FARASTAR Cable Set 
• FARASTAR Stimulation Module Male Cable• FARASTAR Stimulation Module Female Cable• FARASTAR Stimulation Module Y-Cable – Long• FARASTAR Stimulation Module Y-Cable – Short
FARADRIVE Steerable Sheath	FARADRIVE Steerable Sheath

*Sub-components are not tracked for clinical device accountability

A diagram of the FARAPULSE Pulsed Field Ablation System set-up is provided in **Figure 2.2-1**.

Figure 2.2-1: Diagram of FARAPULSE Pulsed Field Ablation System Connections

[figure not shown]
2.2.2 FARAWAVE Pulsed Field Ablation Catheter

The FARAWAVE PFA Catheter is a sterile, single use, over-the-wire, non-deflectable device that is used with the FARASTAR Catheter Connection Cable and FARASTAR Generator to enable delivery of Pulsed Field Ablation energy for irreversible electroporation.

The FARAWAVE PFA Catheter is offered in 2 different sizes (31 mm and 35 mm fully deployed diameters) to accommodate varying PV anatomy. Selection of either catheter will be at the Investigator's discretion.

[figure not shown]
The FARAWAVE PFA Catheter is a multi-electrode catheter that connects electrically to the FARASTAR PFA Generator (**Figure 2.2-2**). It consists of a distal section with electrodes arranged on splines, a shaft section, and a proximal handle with a manually operated deployment control.

Figure 2.2-2: FARAWAVE Pulsed Field Ablation Catheter

The FARAWAVE PFA Catheter has five (5) variably deployable splines. The five splines are undeployed during insertion and removal and during use can deploy continuously from an undeployed state through a partially deployed ("basket-shaped") configuration to a fully deployed ("flower-shaped") configuration with five petals (**Figure 2.2-3**).

Figure 2.2-3: FARAWAVE Pulsed Field Ablation Catheter – Deployed States

Each spline has 1 electrode that is separately wired from the others on that spline to facilitate connection to a mapping or recording system via a cable supplied with the system. The handle includes a flush port for saline infusion, a deployment control knob with a guidewire lumen hub that can be connected to a hemostasis valve and a short cable that terminates in a single connector for attachment to the FARASTAR Catheter Connection Cable. The other end of the Connection Cable attaches to the front panel of the FARASTAR PFA Generator. The Connection Cable is packaged sterile and is single-use only. The PFA energy is delivered from the FARASTAR PFA Generator over the set of ablation catheter electrodes.

In geographies where The FARAWAVE PFA Catheter is commercially available, the device will be used for the study under the investigational IFU and will then be handled according to **Section 13.2**

Additional important information is provided in the Investigational FARAWAVE PFA Catheter IFU regarding precautions, warnings, specific use instructions and procedural steps of the FARAWAVE PFA Catheter.

2.2.3 FARASTAR Catheter Connection Cable

The FARASTAR Catheter Connection Cable is a sterile, single-use device that is used to attach the FARAWAVE Catheter (31mm or 35mm) to the FARASTAR Generator

[figure not shown]

Figure 2.2-4 FARASTAR Catheter Connection Cable

It is 3 meters in length and terminated at both ends with auto-coupling connectors which contain alignment markers to facilitate connections to the FARASTAR Generator and FARAWAVE Catheter. The main cable diameter is approximately 0.318 inches at each end and is fitted with an over molded strain relief where the cable meets with the connectors.

The FARASTAR Catheter Connector Cable comes in two versions, GEN 1 and GEN 2.

The FARASTAR Connector Cable (GEN1) is investigational in North America. The FARASTAR Catheter Connector Cable (GEN1) is commercially available in Europe and approved for use with the FARAWAVE PFA Catheter. When used in Europe in conjunction with the FARAWAVE PFA Catheter, it will be handled according to **Section 13.2**.

The FARASTAR Catheter Connector Cable GEN 2 is investigational and will be used in geographies where the system is not commercially available.

Additional important information is provided in the FARASTAR Catheter Connection Cable IFU regarding precautions, warnings, specific use instructions and procedural steps.

2.2.4 FARASTAR Pulsed Field Ablation Generator

The FARASTAR PFA Generator is a 12-channel output unit that generates a pulsed voltage waveform that can be delivered to the FARAWAVE PFA Catheter. The user selectable voltage options for the FARAWAVE PFA Catheter are 1800V to 2000V in 100V increments. All versions of the FARASTAR PFA Generator consist of the components listed above in **Table 2.2-1**.

The generator utilized will be dependent upon regulatory approval in a specific geography. In geographies where The FARASTAR PFA Generator is commercially available, the commercial version of the generator will be used for the study under the investigational IFU and will then be handled according to **Section 13.2**.

Details regarding the generator are provided in the FARASTAR PFA Generator User Manual.

2.2.5 FARASTAR Recording System Module

The FARASTAR Recording System Module (RSM) is a system component to the FARASTAR Generator. The FARASTAR RSM is a filtering and protection unit meant to be placed in between a patient in the Electrophysiology Lab and other equipment such as a recording system for surface-lead signals (ECGs) and intra-cardiac electrograms (EGMs). The primary function of the FARASTAR RSM is to disconnect the inputs of the EP Lab Recording System from their connections to the patient during PFA delivery. The inputs include diagnostic catheters and surface ECGs. This action reduces the risk of interference to the Recording System inputs during an ablation. The secondary function of

the FARASTAR RSM is to provide Stimulation output connectors for Synchronous Mode PFA delivery.

Details regarding the Recording System Module are provided in the FARASTAR Recording System Module User Manual.

2.2.6 FARADRIVE Steerable Sheath

[figure not shown]
The FARAWAVE Catheter will be used with the FARADRIVE Steerable Sheath.

The FARADRIVE Steerable Sheath consists of two (2) primary components, the Steerable Sheath and the Dilator, which are used together. Both components are sterile and single use only.

The FARADRIVE Steerable Sheath is comprised of a distal steerable section and a shaft section which connect to the handle. The handle includes a knob to control the deflection of the distal tip and a flush port for infusion of saline or contrast. The Dilator is intended for insertion through the sheath lumen and includes a shaped tip for dilation for vascular or chamber access (**Figure 2.2-5**).

In geographies where the FARADRIVE Steerable Sheath is commercially available, the device will be used for the study under the investigational IFU and will then be handled according to **Section 13.2**.

Figure 2.2-5: FARADRIVE Steerable Sheath

Details regarding the sheath are provided in the FARADRIVE Steerable Sheath IFU.

3 Study Objectives and Endpoints

3.1 Study Objective

The objective of the ADVANTAGE AF Study is to establish the safety and effectiveness of the FARAPULSE Pulsed Field Ablation System for treatment of drug resistant, symptomatic persistent atrial fibrillation.

3.2 Primary Safety Endpoint

The primary safety endpoint (PSE) is the proportion of Treatment Subjects and Attempt Subjects with one or more of the following device or procedure-related Composite Serious Adverse Events (CSAEs) following the Index Procedure / Rescheduled Index Procedure or the Re-Ablation Procedure within the Blanking Period, with an Onset Date following the procedure as specified in **Table 3.2-1**:

Table 3.2-1: Primary Safety Endpoint Composite Serious Adverse Events

Composite Serious Adverse Events	Onset Date

 • Death • Myocardial infarction • Stroke • TIA • Peripheral or organ thromboembolism • Pulmonary edema • Unresolved phrenic nerve palsy / paresis • Vascular access complications • Heart block • Gastric motility / pyloric spasm disorders 	Day 0 – Day 7

 • Cardiac tamponade / perforation • Pericarditis 	Day 0 – Day 30

 • PV stenosis • Atrio-esophageal fistula 	Day 0 – Day 360 Assessment

For the analysis of the PSE, CSAEs are only defined for the following procedures that include the use of investigational devices:

- The Index Procedure / Rescheduled Index Procedure (**Section 7.6.1**)
- A Re-Ablation Procedure for AF, AFL or AT within the Blanking Period (**Section 7.13.1**)

Device or procedure-related SAEs related to any other ablation procedure that does not include an investigational device will not be included in the analysis of the PSE, including Other Re-ablation Procedures (**Section 7.13.2**).

3.2.1 Composite Serious Adverse Event Definitions

Each of the adverse events (AEs) comprising a PSE CSAE is specifically defined in **Table 3.2-2**:

Table 3.2-2: Composite Serious Adverse Event Definitions

Related SAE	Description / Criteria
Death	AE resulting in subject death
Myocardial infarction	Defined as the presence of any one of the following criteria: (1) detection of ECG changes indicative of new ischemia (new ST- T wave changes or new LBBB) that persist for more than 1 hour (2) development of new pathological Q waves on an ECG (3) imaging evidence of new loss of viable myocardium or new regional wall motion abnormality

Related SAE	Description / Criteria
Unresolved phrenic nerve palsy / paresis	
A phrenic nerve palsy / paresis is defined as absent or reduced phrenic nerve function assessed as a change in the elevation of a hemi-diaphragm from baseline, that is:
 
 • Not resolved by the end of the procedure • Demonstrated radiographically by pacing, an inspiration / expiration chest X-ray or fluoroscopic sniff test • Not due to a demonstrable pulmonary process such as atelectasis or pleural disease. 
An unresolved phrenic nerve palsy or paresis is defined for this endpoint as not resolved at the time of the last in-person follow-up assessment.

Stroke	
Rapid onset of a focal or global neurological deficit with at least one of the following:
 
 • Change in level of consciousness • Hemiplegia, hemiparesis, numbness, or sensory loss affecting 1 side of the body • Dysphasia or aphasia • Hemianopia, amaurosis fugax, or • Other neurological signs or symptoms consistent with stroke 
The diagnosis of stroke requires that there be no other readily identifiable non-stroke cause for the clinical presentation (e.g., brain tumor, trauma, infection, hypoglycemia, peripheral lesion, pharmacological influences).
 
The duration of the defined neurological deficit(s) must be:
 
 • \geq 24-hours; OR • $<$ 24-hours if 
 ◦ Therapeutic intervention(s) were performed (e.g., thrombolytic therapy or intracranial angioplasty), OR ◦ Available neuroimaging documents a new hemorrhage or infarct, OR ◦ The neurological deficit results in death.
Transient ischemic attack	
Defined as a new focal neurological deficit with:
 
 • Symptom resolution within 24 hours • No new tissue injury demonstrated (if neuroimaging is obtained)
Peripheral or organ thromboembolism	
A cardiac thrombus that occludes a more distal arterial site other than the central nervous system (see Stroke). Cutaneous petechiae are excluded from this definition.

Cardiac tamponade / perforation	
The development of a pericardial effusion post-ablation that results in hemodynamic compromise, requires pericardiocentesis or results in a 1-cm or more pericardial effusion as documented by echocardiography. Cardiac tamponade / perforation should also be classified as “early” or “late” depending on whether it is diagnosed during or following initial discharge from the hospital.

Pericarditis	
The development of pericardial inflammation post-ablation that results in an effusion that leads to hemodynamic compromise or requires pericardiocentesis, prolongs hospitalization by more than 48 hours, requires hospitalization, or persists for more than 30 days following the ablation procedure.

Related SAE	Description / Criteria
Pulmonary edema	Respiratory compromise resulting from cardiac dysfunction or volume overload, leading to increased interstitial lung fluid requiring intubation or parenteral diuretics.
Vascular access complications	Vascular access complication (e.g., groin hematoma, AV fistula, pseudoaneurysm) requiring a significant and invasive intervention (e.g., surgical repair, blood transfusion or thrombin injection).
Heart block	Impairment of AV conduction that is related to a protocol-stipulated cardiac ablation procedure and that requires permanent pacing.
Gastric motility / pyloric spasm disorders	Evidence of impaired gastric motility or pyloric spasm that prolongs hospitalization, requires hospitalization, or persists for more than 30 days.
Pulmonary vein stenosis	>70% reduction of an ablated measured PV diameter compared to the baseline CT / MRI scan, as determined by the Cardiac Imaging Core Laboratory (CICL).
Atrio-esophageal fistula	Confirmation of a fistulous connection between the atrium and the lumen of the esophagus by radiographic, endoscopic, or post-mortem examination

For the purposes of Clinical Event Committee (CEC) adjudication of trial outcomes and the associated analyses of safety endpoints:

- Procedures (such as cardioversion and endocardial ablation) are not adverse events.
- Pre-existing diseases or conditions (including AF, AFL, AT) will not be reported as adverse events unless there has been a substantial increase in severity or frequency of the problem as compared to the subject's baseline which cannot be attributed to the expected progression of the disease or condition
- AEs will be deemed serious according to the criteria and notes in **Section 17**.

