3.4.1 Additional Safety Endpoints

The following endpoints will be descriptively analyzed through the Day 360 Assessment in Treatment Subjects and the Day 30 Assessment in Attempt Subjects:

- **Composite Non-Serious Adverse Events:**
Defined as the proportion of subjects with one or more composite nonserious AEs otherwise as defined in **Table 3.2-2: Composite Serious Adverse Event Definitions**.
- **Related Adverse Events**
Defined as the proportion of subjects with one or more device or procedure-related AEs
- **Any Serious Adverse Event**
Defined as the proportion of subjects with one or more SAEs whether or not device or procedure-related
- **Post-Blanking Arrhythmia Hospitalizations**
Defined as the proportion of Treatment subjects with one or more physician-directed admission to an inpatient hospital facility for at least two consecutive calendar days for the primary purpose of diagnosing or treating AF, AFL or AT beginning after Day 90
- **Post-Blanking Cardioversions**
Defined as the proportion of Treatment subjects with one or more electrical cardioversions for AF, AFL or AT after Day 90

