6.6.4 Attempt Subjects

An Attempt Subject is a subject who signs informed consent, meets eligibility criteria, and has any investigational device inserted into the body but does not receive any pulsed field ablation application.

Attempt Subjects:

- Do not count towards the Treatment Subject enrollment ceiling.
- Will be followed up to the Day 30 assessment with all applicable CRFs completed
- Will be used for analysis of the study safety outcomes
- Will not be used for analysis of the study effectiveness outcomes including subgroup, multivariable, and center pooling analyses.
- Will not be allowed to re-enroll in the study.

For Attempt Subjects, at a minimum the following forms must be completed:

- Enrollment and baseline CRFs such as, but not limited to, informed consent, enrollment information and other related CRFs
- End of Study CRF
- Adverse Event CRFs for any reportable event as defined in **Section 17.1** for any adverse event that occurs after signing the Informed Consent, up to the point of subject withdrawal

The original signed Informed Consent for each Attempt Subject must be maintained in the investigation site's patient file. A subject ID will be assigned in the EDC system.

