7.6.2.1 Preparation

Subjects must be screened for substantial compliance with 4 weeks of systemic anticoagulation prior to the Index Procedure and, if in the opinion of the Investigator, this condition has not been met, the subject will be rescheduled as defined in Section 7.6.3.

TEE or volumetric CT within 48 hours of the procedure or ICE during the procedure will be utilized prior to transseptal puncture for exclusion of LA thrombus. If the study reveals atrial thrombus, the investigational procedure will not begin or will be terminated, no ablation will be performed, and the subject will be rescheduled as defined in Section 7.6.3.

Phrenic nerve function will be assessed prior to ablation per Investigator standard of care, preferably by a pre-sedation fluoroscopic sniff test. Subjects will undergo sedation / anesthesia according to institutional protocol. They will then be prepared in conventional sterile fashion for a cardiac catheterization procedure.

Femoral vein access will be obtained aseptically under ultrasound guidance.

Commercially available diagnostic catheters may be placed before or after transseptal access at the Investigator's discretion. Transseptal access to the LA will be obtained using commercially available devices, establishing guidewire access to the LA.

A heparin bolus will be delivered prior to or immediately after transseptal puncture. Procedural ACTs will be monitored according to the investigational site's standard of care and maintained at a minimum of 300 seconds at least until all devices are withdrawn from the left atrium.

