8.1.1.2 Sample Size

The sample size estimate was obtained using the binomial exact method. The following assumptions were used in the sample size calculation:

Table 8.1-2: Assumptions for the Primary Safety Endpoint Sample Size Estimate

Assumptions	Primary Safety Endpoint
Expected rate	6%
Performance goal	12%
Attrition (per year)	10%
Significance level (one-sided)	0.025
Power	86%
Evaluable subjects	232
Subjects accounting for attrition	258

Under the method and assumption outlined above, the required sample size for this endpoint after attrition is 232, so a minimum of 258 Treatment Subjects are required for the analysis of primary safety endpoint. In addition, all Attempt Subjects will be included in the primary safety endpoint analysis.

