19.2 Clinical Events Committee

A Clinical Events Committee (CEC) is an independent group of individuals with pertinent expertise that will adjudicate events reported by study Investigators and their relationship toward potential primary endpoints.

- All deaths
- All Serious Adverse Events
- All adverse events included in the composite primary safety endpoint per **Section 3.2** of this protocol
- All adverse events that are potentially related to the procedure or any of the devices included in the FARAPULSE PFA System
- All unanticipated device effects.
- Other events at the discretion of BSC

Committee members will include practitioners of Electrophysiology (EP), and / or Cardiology, as well as other experts with the necessary therapeutic and subject matter expertise to adjudicate the event categories outlined above. A complete description of CEC responsibilities, qualifications, membership, and committee procedures will be outlined in the CEC charter.

The CEC will review a safety event dossier, prepared by BSC, which may include copies of subject source documents provided by study sites, core lab results and independent reviewer information as available for the above listed events. For purposes of determining inclusion into the primary safety endpoint, the CEC will adjudicate all the above listed events as to their level of seriousness and relation to the ablation procedure and / or catheter. All supporting source documentation provided by the center will be sent to the CEC for adjudication as defined in the CEC charter. The CEC's adjudication of study adverse event data is final.

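### The tamponade/perforation component of the primary safety endpoint is worded as post-ablation, so on its plain wording it omits a non-fatal perforation that occurs after device insertion but before any energy is delivered

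*Combined protocol and SAP*

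**What the plan says.** Section 3.2 states that the primary safety endpoint (PSE) "is the proportion of Treatment Subjects and Attempt Subjects with one or more of the following device or procedure-related" composite events. Section 8.1.1.2 adds that "all Attempt Subjects will be included in the primary safety endpoint analysis". Section 6.6.4 defines an Attempt Subject as one who meets eligibility and "has any investigational device inserted into the body but does not receive any pulsed field ablation application", followed to Day 30.

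Section 3.2.1 makes the component table binding: "Each of the adverse events (AEs) comprising a PSE CSAE is specifically defined in" Table 3.2-2. The tamponade/perforation row there reads "The development of a pericardial effusion post-ablation that results in hemodynamic compromise, requires pericardiocentesis", or an effusion of at least 1 cm on echocardiography. Its onset window in Table 3.2-1 is Day 0 to Day 30. Appendix A, Table 3.3-2, repeats the row for Phase 2.

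The definitions in Section 23.2 of both phases do not explain *post-ablation*. No section gives a separate component rule for Attempt Subjects.

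**The concern.** Attempt Subjects receive no pulsed field energy, so their place in a safety endpoint is to show harm from inserting and manipulating the investigational sheath and catheter. Perforation is the obvious harm of that kind. If the component needs an ablation to have happened first, a perforation that ends the procedure before the first application leaves the subject in the denominator and the event out of the numerator. The same wording touches a Treatment Subject whose effusion develops before the first application.

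At stake is the rate tested against the 12% performance goal. Any uncounted event lowers that rate, and an undefined term in a primary component leaves the CEC to choose a reading case by case.

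**Working it through.** **1. The plan's own figures.** Exact binomial test, 6% versus 12%, one-sided 0.025. At n = 232 the test passes with at most 18 events (type I error 0.0246) and point power is 89.4%. The stated 86% matches the lowest exact power over all n of 232 or more (86.2%). Attrition: 232/(1 − 0.10) = 257.8, so 258. The design figures reproduce, and the issue below does not change them.

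**2. Does the wording exclude the event?** The documents use the term in two ways.

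| Ablation meaning energy delivery | Post-ablation meaning after the procedure |
|---|---|
| Section 7.6.2.1: if thrombus is found, "the investigational procedure will not begin or will be terminated, no ablation will be performed" | Section 7.3: the post-ablation heading covers anticoagulation after any ablation procedure |
| Section 7.6.1: phrenic function assessed pre and post ablation | Section 6.6.2: Roll-In follow-up of 12 months post-ablation |
| Table 7.17-1: post-ablation electrograms showing block | Table 3.2-2, pericarditis row: post-ablation beside a clause that counts from the ablation procedure |

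The plain wording leaves the event out. The right-hand column makes a lenient reading arguable, but no text adopts it for this row.

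**3. Does another component catch it?**
- Phase 1: pericarditis carries the same post-ablation limit. Vascular access complications are illustrated by groin-type injuries. A related death on Day 0 to 7 would count. No other component describes a non-fatal cardiac perforation.
- Phase 2: Table 3.3-2 adds related cardiovascular or pulmonary events within 30 days that prolong or require hospitalization for more than 48 hours. This may catch some perforations, but not one resolved with a shorter stay.

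**4. Can the CEC repair it?** Section 19.2 says that, for inclusion in the PSE, the CEC "will adjudicate all the above listed events as to their level of seriousness and relation to the ablation procedure" or catheter. It states no power to widen a component definition. The charter is not among the documents.

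**5. Size at the decision boundary.** Inputs: 258 Treatment Subjects and a 12% goal (Section 8.1.1.2), with a Kaplan-Meier log-log 97.5% one-sided upper limit (Section 8.1.1.3). Assumed: no censoring, and 0 to 13 Attempt Subjects (up to 5% of 258), because the documents give no number.

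With x events in N, S = 1 − x/N, θ = √[x/(N(N − x))]/|ln S|, and upper limit = 1 − S^exp(1.96θ).

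For x = 20, N = 258: S = 0.92248, ln S = −0.08069, √[20/(258 × 238)] = 0.018047, θ = 0.2237, exp(1.96θ) = 1.550, limit = 11.76%.

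| N | 20 events | 21 events | 22 events | Most events that pass |
|---|---|---|---|---|
| 258 | 11.76% | 12.21% | 12.66% | 20 |
| 262 | 11.58% | 12.03% | 12.47% | 20 |
| 263 | 11.54% | 11.98% | 12.43% | 21 |
| 271 | 11.21% | 11.64% | 12.07% | 21 |

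One event moves the observed rate by 1/258 = 0.39 points and, at the boundary, turns fail into pass.

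**6. Effect on the type I error.** Suppose the true total rate is 12% and k events are expected to go uncounted. The chance of passing is P(X ≤ c) with X binomial(N, 0.12 − k/N).

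| N, c | k = 0 | k = 1 | k = 2 | k = 3 |
|---|---|---|---|---|
| 258, 20 | 1.8% | 2.8% | 4.2% | 6.3% |
| 263, 21 | 2.4% | 3.6% | 5.3% | 7.7% |
| 271, 21 | 1.6% | 2.4% | 3.7% | 5.4% |

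The values of k are illustrative. The documents give no basis for an expected number.

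**The case against.** The best counter-argument is that Section 3.2 governs. It ties onset to the procedure, opens the window at Day 0, refers to procedures that use investigational devices and names Attempt Subjects. Read with the right-hand column in step 2, *post-ablation* could simply mean after the ablation procedure, and a sheath perforation would count. This stands as a possible reading. It does not settle the matter, because Section 3.2.1 sends the reader to the table for the specific definition and the table uses the narrower word.

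Three stronger readings are tempting, and the documents do not support them.
- A reader might infer that an Attempt Subject can never meet the component. Attempt status turns on pulsed field applications only. CTI ablation uses a radiofrequency catheter (Section 7.6.2.5) and the sequence may be altered for subject welfare (Section 7.6.2), so an earlier radiofrequency lesion is not ruled out.
- A reader might infer that the injury disappears from the trial. It does not. Section 3.4.1 reports Related AEs and Any SAE ("Defined as the proportion of subjects with one or more SAEs whether or not device or procedure-related") for Attempt Subjects to Day 30, and the CEC adjudicates all SAEs. Only the tested endpoint may miss it.
- A reader might infer a demonstrated downward bias. No count of such events or of Attempt Subjects is given.

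The exposed interval is also short. Transseptal access uses commercially available devices (Section 7.6.2.1). A perforation before any investigational device is inserted, if the case then stops, makes an Intent Subject, outside the PSE under either wording.

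Finally, the 6% and 12% come from a meta-analysis said to use the events that constitute this PSE. Whether the source studies counted perforations before energy delivery cannot be told from the documents.

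**Conclusion.** The definition and the analysis population do not fit together. On the plain wording, a non-fatal perforation between insertion of an investigational device and the first application is outside the tested endpoint. In Phase 1 nothing else non-fatal in the composite catches it; in Phase 2 some cases may be caught.

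The practical size is small. The plan expects about 0.06 × 258 = 15.5 events, below the boundary, and few would be of this kind. The effect is concentrated at the boundary, where a single uncounted event decides the result. This rests on no censoring and an assumed 0 to 13 Attempt Subjects. It is an ambiguity that could favour the device, not proof of a biased result, and it is worth settling before events are adjudicated.

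**What to change.** In Table 3.2-2 and Table 3.3-2, replace *post-ablation* in the tamponade/perforation row with: *from insertion of an investigational device onward, during or after the Index, Rescheduled Index or qualifying Re-Ablation Procedure, whether or not any ablation was delivered*. A qualifying re-ablation is one that Section 3.2 (Phase 1) or Appendix A Section 3.3 (Phase 2) already counts.

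Put the same reading in the CEC charter. This is needed for Phase 1 because Appendix A Section 4.1.1 has those subjects analyzed under the protocol version in which they enrolled, so a table edit alone may not govern them. If any case has already been adjudicated on the narrow reading, list it and show the PSE both ways.

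The cost is one phrase in two tables and a charter clarification. Sample size, performance goal and visits do not change. The downside is that the observed event rate may rise slightly, by 0.39 points per added event at N = 258.
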